## **7.2. Expected number of subjects to be included.**

Group sample size of 121 in Group 1 and 121 in Group 2 achieve 80% power to detect a difference between the group proportions of 0,1240. The proportion in Group 1 (the treatment group) is assumed to be 0,8 under the null hypothesis and 0,9240 under the alternative hypothesis. The proportion in Group 2 (the control group) is 0,8000. The test statistic used is the two-sided Z test with pooled variance. The significance level alpha of the test was 5 %. To account for a drop out rate around 20%, sample size of 121 in each group, overall  $n=242$  women will be recruited.

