#### **4.10. 3. Withdrawal criteria.**

If a participant may voluntarily withdraw from treatment or if it is necessary to remove the pessary due to the conditions described before, the patients will be followed as usual until delivery (intention-to-treat analysis).

Replacement of patients is not applicable in this trial.

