## **7.4. Selection of subjects to be included in each analysis.**

The analysis will include all the subjects that have been randomised.

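### The 121 per group said to cover about 20% dropout is the uninflated sample size, so 242 holds no allowance; power is about 71% if 20% have no primary outcome

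*Protocol*

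**What the plan says.** Protocol section 7.2 opens with the power statement: "Group sample size of 121 in Group 1 and 121 in Group 2 achieve 80% power to detect a difference between the group proportions" of 0.124, with 0.80 in the control group and 0.924 in the pessary group under the alternative. The test is specified: "The test statistic used is the two-sided Z test with pooled variance", at a 5% significance level. The same paragraph closes with "To account for a drop out rate around 20%, sample size of 121 in each group" and a total of 242 women to be recruited. No smaller number before dropout appears anywhere in the protocol.

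Two other sections bear on what a dropout would cost:

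- Section 4.10.3, on women who withdraw from treatment or have the pessary removed: "the patients will be followed as usual until delivery (intention-to-treat analysis". It adds "Replacement of patients is not applicable in this trial".
- Section 7.4: "The analysis will include all the subjects that have been randomised".

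**The concern.** A dropout allowance makes the number recruited larger than the number that must be analysed. Here the two are identical. Either 121 is the number to be analysed and there is no allowance, or 121 is the inflated number and a smaller group delivers the 80% power. The arithmetic has to decide which.

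What is at stake is a stated design property. Ethics committees and readers are told that 80% power is protected against losses of about 20%. If it is not, every missing primary outcome takes power below 80%, and because replacement is excluded the losses cannot be made good. The meaning of dropout matters too: section 7.2 does not say whether it means stopping treatment or having no outcome, and only the second reduces the number analysed.

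**Working it through.** **Inputs (all from section 7.2).** p1 = 0.924, p2 = 0.800, difference 0.124; two-sided alpha 0.05 (z = 1.960); power 80% (z = 0.8416); pooled-variance Z test; equal groups. I take the proportions to refer to the primary outcome, as is usual for a sample size.

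**Step 1: reproduce the 121.** The mean proportion is (0.924 + 0.800)/2 = 0.862.

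- Null term: √(2 × 0.862 × 0.138) = √0.237912 = 0.48776
- Alternative term: √(0.924 × 0.076 + 0.800 × 0.200) = √0.230224 = 0.47982
- n = [(1.960 × 0.48776 + 0.8416 × 0.47982) / 0.124]² = [(0.95600 + 0.40382) / 0.124]² = 120.26

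Rounded up, this is 121 per group, an exact match. Power is 79.9% at 120 and 80.2% at 121, so 121 is the minimum number analysed.

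**Step 2: test whether 121 could be the inflated number.** Taking 20% off gives 121 × 0.8 = 96.8, or 97 per group. Power = Φ[(0.124 × √97 − 0.95600) / 0.47982] = Φ(0.553) = 71.0%. So 97 is not a base with 80% power. Exact binomial enumeration of the same test agrees: 81.6% at 121 and 72.6% at 97.

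**Step 3: try other routes to 121.**

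| Variant | n per group | After 20% inflation |
|---|---|---|
| Two-sided, pooled (as stated) | 121 | 121/0.8 = 151.25, so 152 |
| Two-sided, unpooled | 118 | 148 |
| Two-sided, continuity-corrected | 136 | larger still |
| One-sided 5%, pooled | 95 | 119 |

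Only the one-sided route comes near 121 after inflation. It is ruled out: sections 7.1 and 7.2 both specify a two-sided test, and section 7.2 attributes 80% power to 121 itself.

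**Step 4: what 242 women deliver.** The share with no primary outcome is an assumption, taken as equal in both groups.

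| Share missing | Analysed per group | Power for 0.80 v 0.924 | Difference from 0.80 needed for 80% power |
|---|---|---|---|
| 0% | 121 | 80.2% | 0.124 |
| 5% | 115 | 78.2% | 0.126 |
| 10% | 109 | 76.0% | 0.129 |
| 15% | 103 | 73.6% | 0.132 |
| 20% | 97 | 71.0% | 0.135 |

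**The case against.** The best reply is that dropout hardly matters here. Women who stop treatment are followed to delivery and all randomised women are analysed, so most dropouts would still contribute an outcome, and 71% is the far end of the range. This is right as far as it goes: with complete outcomes the 80% stands, and the lower figures are conditional. It does not rescue the sentence in section 7.2, which claims an allowance that does not exist.

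Three further points deserve an answer.

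- Section 5.3 requires an end-of-study assessment for women taken off treatment because of an adverse event, which could be read as ending their participation. It does not cancel the explicit follow-up in section 4.10.3 or the all-randomised analysis in section 7.4. If it did lead to lost outcomes, power would fall as tabulated.
- Section 7.2 does not name the outcome behind 0.80 and 0.924. Reading them as primary-outcome proportions is conventional, and the contradiction over 121 holds whichever outcome is meant.
- The sponsor may have wanted a real allowance, in which case recruiting more women is the other route. That is true, but it is not a cheap change; correcting the statement is.

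The definition of dropout could sit in an SAP, so its absence is not counted as a separate defect.

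**Conclusion.** The point holds. Section 7.2 uses one number for two incompatible purposes, and the arithmetic shows that 121 per group is the uninflated requirement. The 242 women therefore contain no dropout allowance. Loss of power runs from about 2 percentage points at 5% missing to about 9 at 20% missing (80.2% to 71.0%). At 20% missing, the chance of failing to detect the assumed effect rises from about 20% to 29%.

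These figures rest on the protocol's own proportions, test and alpha, and on equal missingness in the two groups. Type I error and the validity of the comparison are untouched. I make no claim about dilution of the effect by stopped treatment, because the protocol does not say whether 0.924 assumes full adherence or is an intention-to-treat proportion. The sentence should be corrected, but the design is not invalid.

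**What to change.** In section 7.2, delete the claim that 121 per group accounts for dropout and replace it with wording such as:

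> 242 women (121 per group) will be randomised. With complete primary outcome data, power is 80% for 0.80 versus 0.924 (two-sided pooled Z test, alpha 5%). This number includes no allowance for missing outcomes: if 5%, 10% or 20% of women have no primary outcome (about 115, 109 or 97 per group), power is about 78%, 76% or 71%. Women who stop treatment are followed to delivery and analysed as randomised; they do not count as dropouts here.

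The cost is one paragraph of protocol text and a less favourable stated power. No extra patients are needed, and the test, alpha and analysis set do not change. For reference only, keeping 80% power with 20% of outcomes missing would need 121/0.8 = 151.25, so 152 per group and 304 in total, which is 62 more women than planned.

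### The 121 women per arm make no allowance for the 20% drop-out that section 7.2 says they account for; depending on what drop-out means, power is about 71%, or between 58% and 80%

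*Protocol*

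**What the plan says.** Protocol section 7.2 states: "Group sample size of 121 in Group 1 and 121 in Group 2 achieve 80% power". The difference on which this rests is 0.124. The treatment-group proportion is "0,8 under the null hypothesis and 0,9240 under the alternative hypothesis", and the control proportion is 0.80. On the test it says: "The test statistic used is the two-sided Z test with pooled variance". On the error rate it says: "The significance level alpha of the test was 5" per cent. The paragraph closes by giving 121 per group, 242 in all, as the recruitment figure "To account for a drop out rate around 20" per cent. It does not say what counts as a drop-out, or in which arm.

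Two other sections decide what happens to women who leave treatment. Section 4.10.3 covers voluntary withdrawal from treatment and early removal of the pessary, and says "the patients will be followed as usual until delivery (intention-to-treat analysis"); it also rules out replacement. Section 7.4 says: "The analysis will include all the subjects that have been randomised". Section 5.3 separately mentions adverse events that lead to withdrawal from the study, so leaving the study altogether is also foreseen.

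**The concern.** The same number serves as the requirement for 80% power and as the recruitment target after a 20% allowance. Both can be right only if the requirement without drop-out is clearly below 121, or if the 20% has no effect on power.

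There is a second difficulty. The sentence treats drop-out as a matter of head count. Under 4.10.3 and 7.4, women who stop treatment are not lost to the analysis: they stay in their randomised arm and may pull its result towards the control rate. Recruiting more women by the usual inflation does not fully repair that, because the difference under test has become smaller.

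What is at stake is how a non-significant result would be read. A reader told that power is 80% takes the chance of missing the assumed effect to be 20%. At 71% power it is 29%, and at 58% it is 42%.

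**Working it through.** **Inputs.** All from section 7.2: p1 = 0.924, p2 = 0.80, difference d = 0.124, n = 121 per arm, two-sided 5% (z = 1.960), 80% power (z = 0.842), Z test with pooled variance, drop-out 20%. The outcome rate in women who stop treatment is not given and has to be assumed.

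**Formulas.** With p̄ = (p1 + p2)/2, S0 = √[2p̄(1 − p̄)] and S1 = √[p1(1 − p1) + p2(1 − p2)]:

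- n per arm = [(1.960·S0 + 0.842·S1)/d]²
- power = Φ[(d√n − 1.960·S0)/S1]

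**Step 1: reproduce the plan's figure.** p̄ = 0.862, S0 = 0.4878, S1 = 0.4798.

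- n = [(0.956 + 0.404)/0.124]² ≈ 120.3, rounded up to 121.
- Power at 121 = Φ[(1.364 − 0.956)/0.4798] = Φ(0.850) = 80.2%.

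The stated 121 is matched exactly with no drop-out in the calculation. The usual inflation would have given 121/0.8 = 151.25, that is 152 per arm or 304 in all.

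**Step 2: drop-out means lost outcomes.** 121 × 0.8 = 96.8, about 97 per arm. Power = Φ[(1.2213 − 0.956)/0.4798] = Φ(0.553) = 71.0%.

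**Step 3: drop-out means stopping allocated treatment, with all 121 per arm analysed.** Assumptions: 0.924 applies to women who keep to treatment; 20% of the pessary arm stop; a woman who stops keeps a share r of the benefit; the control arm stays at 0.80. The pessary-arm proportion is then 0.80 + 0.124 × (0.8 + 0.2r).

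| Benefit kept, r | Pessary arm | Difference | Power at 121 per arm |
|---|---|---|---|
| 0 | 0.8992 | 0.0992 | 57.9% |
| 25% | 0.9054 | 0.1054 | 64.0% |
| 50% | 0.9116 | 0.1116 | 69.8% |
| 75% | 0.9178 | 0.1178 | 75.2% |
| 100% | 0.9240 | 0.1240 | 80.2% |

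First row in full: p̄ = 0.8496, S0 = 0.5055, S1 = 0.5006; power = Φ[(1.0912 − 0.9908)/0.5006] = Φ(0.201) = 57.9%.

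With no benefit kept but fewer women stopping, power is 75.2% at 5%, 69.8% at 10% and 64.0% at 15%.

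**Step 4: would the usual inflation have been enough?** For lost outcomes, yes: 152 × 0.8 = 121.6, which restores the requirement. For treatment stops with no benefit kept, no: at 152 per arm and 0.8992 versus 0.80, power = Φ[(1.2230 − 0.9908)/0.5006] = Φ(0.464) = 67.9%. About 203 analysed per arm would be needed for 80%.

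**The case against.** A reader might infer that power is simply 58% instead of 80%. The documents do not support that. It requires four things that the protocol does not state: every drop-out is a treatment stop, women who stop keep no benefit, the control arm does not change, and 0.924 is a full-adherence rate. Each can fairly be disputed.

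- **Meaning of drop-out.** Treatment withdrawal is not the only form of leaving that the protocol describes, because section 5.3 mentions withdrawal from the study. Lost outcomes are an ordinary reading of the term, and then the sample does shrink.
- **Benefit kept.** A pessary worn for some weeks may have done part of its work. Section 4.6 lists membrane rupture after 34+0 weeks as one reason for removal. Section 7.2 names no endpoint, but if it is birth before 34 weeks (the first row of the table in 7.1), those women have already passed it. Women whose pessary is removed for persistent contractions may already be among the assumed 7.6% failures. Giving all of them a success rate of 0.80 could misstate them.
- **Control arm.** Section 7.2 does not split the 20% by arm. Control women who stop could also have a different success rate, so the net difference is not known.
- **Status of 0.924.** It may already be the intention-to-treat proportion. Nothing in 7.2 says either way.

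All of this stands against 58% as a point estimate. It does not rescue the sentence in 7.2. If outcomes are lost, power is about 71%. If women stop treatment and lose some of the benefit, it is below 80%. If 0.924 already includes women who stop, 80% can stand, but then 121 contains no separate allowance for them and the claim to have made one is still wrong.

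**Conclusion.** Section 7.2 is wrong as written. That 121 per arm contains no allowance for 20% drop-out is certain and needs no assumption, since the plan's own inputs give 121 before any drop-out.

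The effect on power depends on a definition that the protocol does not give. It is about 71% if the 20% are lost outcomes. If they are treatment stops under intention-to-treat, the range is 58% to 80%, according to the benefit kept. That range assumes that 0.924 is a full-adherence rate and that the control arm is unaffected. The 58% is its low end and should not be quoted alone.

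**What to change.** Rewrite the drop-out sentence in section 7.2:

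1. Say whether the 20% means stopping allocated treatment or loss of outcome data, and give the two separately if both are expected.
2. Say whether 0.924 already includes women who stop treatment.
3. Remove the claim that 121 per arm includes a 20% allowance.
4. Replace the unqualified 80% with the power of the analysis laid down in 4.10.3 and 7.4: about 71% with about 97 evaluable per arm if outcomes are lost, or 58% to 80% with its assumptions if women stop treatment. If 0.924 is declared to be the intention-to-treat proportion, 80% may stay for treatment stops, and loss of outcomes is then dealt with on its own.

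Keep the 242 women and the intention-to-treat analysis. The change is one paragraph, with no added patients or procedures. The cost is a less favourable stated power.

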## **7.3. Criteria for the completion of the trial.**

A non-justified case of maternal death (temporary stop until complete evaluation of the case by an external committee).

## **7.4. Selection of subjects to be included in each analysis.**

The analysis will include all the subjects that have been randomised.

## **8. Quality and Control Assurance**

Main investigator and collaborators: In order to ensure the Quality of the data they will provide instructions and training to the sites involved in the trial; review the CRF data; and detail of any other steps taken to ensure quality of research.

The main investigator will sign the study protocol and the “investigator’s commitment; he will apply for the Ethics Committee and the Director’s approval; and he will review the final report of the study.

The collaborators will assess patient’s eligibility, they will inform the patients and ask for the informed consent; and they will be responsible of the CRF and obtaining and registering all data.

Monitor: he will perform regular monitoring according to ICH GCP. Data will be evaluated for compliance with the protocol and accuracy in relation to source documents. Monitors will verify that the clinical trial is conducted and data are generated, documented and reported in compliance with the protocol, GCP and the applicable and local regulatory requirements.

Serious Breaches: A serious breach is defined as “A breach of GCP or the trial protocol which is likely to effect to a significant degree: (a) the safety or physical or mental integrity of the subjects of the trial; or (b) the scientific value of the trial”. All serious breaches will be notified to the competent Regulatory Authority according to applicable legislation.

## **9. Ethical issues**

The Sponsor, participating Centres and Investigator will ensure that this study is conducted in accordance with the Protocol, the principles of the Declaration of Helsinki (see annex III), ICH Guidelines for Good Clinical Practice and in full conformity with relevant regulations as well as applicable national laws, the German Law and in accordance with regulations and guidelines applicable to clinical trials relating to medical devices.

The protocol, informed consent form, participant information sheet and any applicable documents will be submitted to an appropriate Ethics Committee (EC) and Regulatory Authority for written approval. All substantial amendments to the original approved documents will be also sent to an appropriate Ethics Committee (EC) and Regulatory Authority for written approval. The study will not begin until the approval of the EC and Director’s consent.

## **10. Data Management and Registry File**

Patient's participation in the study will be annotated into the medical history. The main investigator will perform a list with the participant's names, ID numbers and codes. He also will have a file with all the information referring to the study. All the data will be collected in a database that will be accessed worldwide. The randomisation will be done on a computer basis. Once entering in the website, if the patient fulfils the inclusion criteria, the computer generated list will randomise the patient to "pessary" or "control" group. The excluded patients will be also collected in the database. Every participating centre will have its own randomisation list, and it will be accessible with a username and password. The trial staff will ensure that the participants' anonymity is maintained. Only a participant ID number on the CRF and in the electronic database will identify the participants. All documents will be stored securely and only accessible by trial staff and authorized personnel. The study will comply with the Data Protection Legislation that requires data to be anonymized as soon as it is mandatory to do so.

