#### 4.2. Description of the trial design.

Open Multicentre Randomized Controlled Trial, in parallel groups, based on treatment with progesterone comparing the placement of a prophylactic cervical pessary with usual management in singleton pregnancies at high-risk of PTB due to a history of at least one previous preterm delivery and/or a history of late abortion.

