## **7. Statistics**

### **7.1. Description of statistical methods.**

A descriptive analysis by preterm birth will be carried out calculating means and medians for quantitative variables and proportions for categorical variables.

Two-sided Z-tests will be used for comparing among exposure and outcomes groups per pregnancy. A multivariate logistic regression will be fitted to control for possible confounders. Relative risks and 95% confidence interval will be calculated for the outcomes.

All analysis will be carried out with SPSS® 19.0 statistical package (IBM Company SPSS Inc. Headquarters, Chicago, Illinois. USA). Statistical significance will be accepted in all cases with a  $p < 0.05$ .

Outcome	Statistical Test
Birth before 34 Weeks of Gestation	Two-sided Z-Test (RR, 95% CI)
Time to Birth	Log-rank test (HR, 95% CI)
Birthweight	Multilevel model (mean $\pm$ SD)
Fetal / Neonatal Death	Two-sided Z-Test (RR, 95% CI)
Neonatal Morbidity	Two-sided Z-Test (RR, 95% CI)
Need for Hospitalization	Two-sided Z-Test (RR, 95% CI)
Days of Hospitalization	Two-sided Z-Test (RR, 95% CI)
Maternal Adverse Events	Two-sided Z-Test (RR, 95% CI)
Pessary Intolerance	Two-sided Z-Test (RR, 95% CI)
Vaginal Infections	Two-sided Z-Test (RR, 95% CI)

the complete data set for the secondary endpoints will be available after the last women enrolled in this study has given birth, so the analysis of these outcome parameter will be done right after this event.

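### Allocation is by centre but the listed tests ignore centre: at worst slightly conservative, with a little power given up

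*Protocol*

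**What the plan says.** Section 4.2 describes an "Open Multicentre Randomized Controlled Trial, in parallel groups". Section 10 adds that "Every participating centre will have its own randomisation list". It says the lists are computer-generated, but not whether they are blocked, what the block size is, or how many centres take part.

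Section 7.1 states that "Two-sided Z-tests will be used for comparing among exposure and outcomes groups per pregnancy". Its table of outcomes and tests has ten rows. Eight carry a two-sided Z test, starting with "Birth before 34 Weeks of Gestation". Time to birth has a log-rank test with no strata named. Birthweight has a multilevel model whose levels are not stated. The section also says that "A multivariate logistic regression will be fitted to control for possible confounders", without listing covariates.

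Section 7.2 sizes the trial on the same comparison: "The test statistic used is the two-sided Z test with pooled variance". Centre does not appear in that calculation.

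**The concern.** When each centre has its own list, centre is part of the randomisation, and an analysis that follows the randomisation compares women within centres. The tests in 7.1 treat all women as if they came from one list.

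Baseline risk and background care could plausibly differ between sites. Rescue cerclage is left to judgement (4.10.4), the rest of care is usual management (4.4, 4.11.1), and the text refers both to Chinese practice (4.4) and to centres under other countries' laws (11).

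If allocation is also balanced within centre, centre differences cancel from the arm difference but remain in the variance that the Z test uses. The interval is then too wide and the test rejects too rarely. At stake is some power in a trial planned with almost none to spare. There is also no within-centre estimate of the effect.

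**Working it through.** **1. The plan's own figure.** Inputs from 7.2: 0.924 versus 0.80, two-sided alpha 5%, power 80%, pooled variance. The mean proportion is 0.862.

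n = [1.960·√(2·0.862·0.138) + 0.8416·√(0.924·0.076 + 0.80·0.20)]² / 0.124²
= [1.960·√0.2379 + 0.8416·√0.2302]² / 0.015376 ≈ 120.3, so 121 per arm.

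Power at 121 is 80.2%. The stated size is reproduced with no centre term.

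**2. Size of the Z test when lists are balanced within centre.** With equal-sized centres and event rates p_c of mean p̄, the true null variance of the arm difference is smaller than the assumed one by the factor

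r = mean[p_c(1 − p_c)] / [p̄(1 − p̄)], so true alpha = 2·[1 − Φ(1.96/√r)].

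The centre rates below are assumptions. They are failure rates averaging 20%, the complement of the 0.80 in 7.2.

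- Large spread, 5/10/25/40%: mean p(1 − p) = (0.0475 + 0.09 + 0.1875 + 0.24)/4 = 0.14125. Then r = 0.14125/0.16 = 0.883, 1.96/√r = 2.086, and alpha is about 3.7%. The standard error is overstated by about 6%.
- Moderate spread, 10/15/25/30%: mean = 0.15375, r = 0.961, and alpha is about 4.6%.
- No spread: r = 1 and alpha is 5.0%.

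A 20,000-run simulation with four centres (arms of 30/30/31/30, balanced within centre) took a relative risk of 0.076/0.20 = 0.38:

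- Large spread: alpha 3.9% for the Z test against 5.1% stratified; power 82.2% against 84.0%.
- Moderate spread: power 81.7% against 82.3%.
- Equal rates: power 82.1% against 81.9%.

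**3. Varying the number of centres and the type of list.** This used 100,000 runs, all 242 women analysed, and equal-sized centres. The assumed SD of the centre log-odds was 0, 0.5 or 1.0. With five centres, SD 0.5 means success rates of about 0.67–0.90 and SD 1.0 about 0.55–0.96. Z is the unstratified test; CMH is the Cochran-Mantel-Haenszel test stratified by centre.

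| Centres | SD | Lists | Alpha Z / CMH | Power Z / CMH |
|---|---|---|---|---|
| 5 | 0 | balanced | 0.050 / 0.049 | 0.815 / 0.814 |
| 5 | 0.5 | balanced | 0.046 / 0.049 | 0.820 / 0.826 |
| 5 | 1.0 | balanced | 0.037 / 0.050 | 0.829 / 0.853 |
| 10 | 1.0 | balanced | 0.036 / 0.050 | 0.830 / 0.856 |
| 5 | 0 | unblocked | 0.049 / 0.049 | 0.813 / 0.806 |
| 5 | 0.5 | unblocked | 0.052 / 0.051 | 0.816 / 0.819 |
| 5 | 1.0 | unblocked | 0.051 / 0.050 | 0.815 / 0.844 |
| 10 | 0 | unblocked | 0.050 / 0.050 | 0.813 / 0.797 |

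By the formula in step 2, SD 1.0 gives alpha of 0.035–0.037 across 2, 5 and 10 centres.

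**4. What the table shows.** The error rate moves only with balanced lists and differing centres, and then only downwards. Stratifying gains power when centres differ strongly, whichever way the lists are built. If centres are alike, it changes nothing material with balanced lists. With ten unblocked lists it costs about 1.6 points (0.813 to 0.797), which is why small strata need a rule.

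**5. Events per stratum.** The planned rates imply 121 × 0.076 ≈ 9 failures in the pessary arm and 121 × 0.20 ≈ 24 in the control arm. Spread over five centres, that is about 2 and 5 per centre.

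**The case against.** The strongest reply is that separate lists do not by themselves mean balance. The protocol states no blocking, and with unblocked lists the Z test keeps its size whatever the centre spread. That stands, and it is why any statement about the error rate has to be conditional.

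A second reply is that 7.1 leaves room for centre in the logistic regression and the multilevel model, and that covariates are commonly named in an SAP, which is not shown. This stands for those two models. It does not cover the tests that 7.1 itself lists for most outcomes, or the calculation in 7.2.

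Three stronger readings are tempting, and the document supports none of them:

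- A reader might infer that the 5% level is simply wrong, or that false positives become more likely. No scenario examined shows material inflation; where the level clearly moves, the test is conservative.
- A reader might count differences in pessary fitting among the variation that stratification removes. Fitting affects one arm only, so it is a treatment-by-centre effect. A Mantel-Haenszel analysis with a common effect does not remove it. Section 8 also provides for training of the sites.
- A reader might take the word pooled in 7.2 to mean pooling of centres. It refers to the variance estimate under the null.

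**Conclusion.** The mismatch is in the text: allocation is by centre, while the listed tests and the sample size ignore centre. The consequence is small. With lists balanced within centre and centres that differ in baseline risk or usual care, true alpha is about 4.6% for moderate differences and about 3.5–3.9% for large ones. The power given up against a stratified test is under 1 point and about 2–3 points respectively. If centres are alike, nothing material is lost.

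These figures rest on assumed centre numbers, equal centre sizes and assumed spreads, none of which the protocol gives. They also assume a common treatment effect across centres and no loss to follow-up. This is a minor point about efficiency and about matching the analysis to the randomisation. It does not threaten the validity of a positive result.

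**What to change.** - **Section 7.1:** for the binary outcomes compared between arms, replace the unstratified Z test by a Mantel-Haenszel test stratified by centre, reporting a common relative risk with its 95% confidence interval. Stratify the log-rank test for time to birth by centre.
- **Small centres:** because few events are expected per centre, write down before data lock a rule for combining small centres. Without one, many thin strata could cost the power that stratifying is meant to save.
- **Section 7.2:** note that 121 per arm was computed with the unstratified Z test. This is a slightly conservative approximation to the stratified test when lists are balanced within centre and centres differ. Without this note, 7.1 and 7.2 would name different tests.
- **Section 10:** state how the lists were built, in particular whether they are balanced within centre.

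The cost is wording only. Centre is already known from the randomisation lists, and no extra data, visits or women are needed.
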